F21. Medical Board for adjudication (aka Expert Panel): A Medical Board will be created by the Coordinating Center and will be composed of three physicians that will be qualified by training, certification, and/or experience as critical care specialists, pulmonologists, and/or intensivists. The Board will review submitted data without the knowledge of HLA antibody status of the transfused blood components. Two members of the Board will review each case and if there is an agreement regarding diagnosis, the case will be assigned the agreed upon diagnosis. If there is a disagreement between the members, then such cases will be discussed during periodic conference calls of the Board to arrive at an adjudicated diagnosis. These conference calls may be attended by the REDS-II investigators. The Board will be asked to make a determination of the case as: 1. TRALI: classified by whether or not other risk factors for acute lung injury are present or not; 2. Acute lung injury (ALI); 3. Transfusion-related cardiac overload (TACO); 4.TRALI/TACO (overlap cases); and 5.Other (e.g. transient hypoxemia due to transient airway obstruction at bronchoscopy or extubation or other causes of transient hypoxemia). These categories will allow cases to be grouped either by the Canadian Consensus Conference definition or the NHLBI Working Party definition, which differ only slightly. For cases that are assigned a diagnosis of other, the Board may be able to assign a more specific diagnosis such as Febrile Non-Hemolytic Transfusion Reaction (FNHTR), bacterial sepsis, etc. Each member of the Board will record their diagnosis on the Expert Review Log Form (Appendix I) and fax it to the coordinating center.

F22. Deaths identified during record review: If during hypoxemia review or detailed chart review, deaths occurring within 24 hours after completion of the study unit transfusion are identified, they will be recorded in the data collection form along with the reason/cause of death. This will occur whether or not the case goes on to further record review. Such deaths along with deaths occurring within 24 hours of transfusion of the study unit in which TRALI, TACO or other serious adverse transfusion reaction is a possibility will also be recorded in the data collection form.

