- 3. For definition of left atrial hypertension, one or more of the following criteria must be present: EKG evidence for recent MI, echocardiogram indicative of heart failure or an ejection fraction <50%, a plasma troponin value greater than the upper reference range of the laboratory, a plasma brain natriuretic peptide of >100 pg/mL, pulmonary edema fluid/plasma fluid protein ratio less than 0.60, and pulmonary artery diastolic pressure or pulmonary artery wedge pressure of 18 mm Hg or more.

In addition to the above, clinical criteria for congestive heart failure, e.g., elevated jugular venous pressure, presence of S3 and S4 sound on auscultation, hepatojugular reflux, and excess input of fluid compared to output, and response to diuretic will be considered in order to differentiate TACO from TRALI.

- 4. No pre-existing acute lung injury before transfusion
- 5. No temporal relationship to an alternate risk factor for acute lung injury
 - Note: Recipients who meet the above criteria but also have a clear relationship to an alternate risk factor for acute lung injury will be considered to have possible TRALI. Also, in accordance with the NHLBI definition, such cases will be classified as TRALI with other risk factors for acute lung injury, provided that the expert panel determines that transfusion is the most likely cause of the ALI. ALI risk factors could be those that cause direct lung injury or those that cause indirect lung injury. Factors that cause direct lung injury are: aspiration, pneumonia, toxic inhalation, lung contusion, and near drowning. Factors that cause indirect lung injury are severe sepsis, shock, multiple trauma, acute pancreatitis, cardiopulmonary bypass, and drug overdose.

6. If the chest x-ray report review indicates absence of bilateral pulmonary infiltrates, the cases will be designated as "Not TRALI".

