G2. Two Consensus Definitions of TRALI: The Finlay study estimated TRALI risk by including TRALI cases with and without other risk factors for acute lung injury (ALI) based upon diagnostic criteria that were developed by the NHLBI Working Group. Another consensus definition has been developed by the Canadian Consensus Conference Group which classified "TRALI with other risk factors for ALI" as "possible TRALI". For research purposes, we believe that in order to better characterize the incidence of TRALI (and not underestimate it), we should include "TRALI cases with other risk factors for ALI" when estimating our overall TRALI incidence. The identification of all possible TRALI cases would give the health care professional a more accurate picture of the potential for TRALI and will allow better decisions concerning the costs and benefits associated with various preventive steps that may be envisioned. Our data collection form will permit classification by both the Canadian Consensus Conference and the NHLBI working group criteria and will permit a comparison of cases diagnosed by these two slightly different definitions.

G3. Generalizability of Finlay's data to the proposed study setting: Since certain blood components (e.g. Plasma, Apheresis Platelets) are more likely to cause TRALI, it is important to review whether the blood component mix transfused at UCSF Medical Center (47% were RBCs, 34% FFPs, 15% apheresis platelets, 4% others) is similar or not to what could be expected at hospitals associated with the REDS-II centers. We have therefore reviewed published data on blood component utilization for various types of hospitals. The data shown below in Table-10 include the results from the US Department of Health and Human Services (DHHS) which had funded a nationwide blood collection and utilization survey in 2005.

As shown in **Table-10**, the data from 2001 described by Novis et al. show that among small hospitals, platelet concentrates derived from whole blood continue to be used. However, these data are now seven years old and in the intervening period, the use of apheresis platelets has grown and that of platelet concentrates from whole blood has decreased nationally. The DHHS data (**Table-10**) provide evidence for this change in transfusion practice.

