- the proportion of TRALI due to HLA antibodies (i.e. immune-mediated)

Additional analyses will involve estimating TRALI incidences and other incidences. Analysis will be conducted to assess the incidence of TRALI and possible TRALI per unit transfused and per transfusion recipient. For this analysis the number of units transfused per episode per patient will be derived from the data available in the data collection forms. Incidence will also be calculated, when possible, for (a) TRALI without other risk factors and TRALI with other risk factors, (b) among those with other risk factors, incidence will be calculated for ALI which cannot be distinguished from TRALI and for ALI that is not TRALI but that occurred within 6 hours or >6 hours of transfusion.

Analysis of other incidences is described below. In addition to the transfusion complications described above, incidence for transfusion-associated cardiac overload will be based on cases that are classified by the Medical panel as TACO.

Using appropriate statistical methods, associations will be explored between different transfusion complications described above (TRALI, no-TRALI, possible TRALI, ALI of undetermined origin, TACO) and the underlying clinical information, such as, demographics, diagnosis (CPT codes), co-morbid conditions (e.g. renal failure), degree and severity of hypoxemia, chest x-ray and cardiac abnormalities. Data, when available, will be correlated with the presence of HLA and HNA antibodies (signal strength and/or specificity of antibodies) in the recipients as well as the involved donors and their HLA and HNA phenotypes to assess the antibody specificity and the corresponding cognate antigens in donor/recipient pairs among different groups of patients with complications described above. Frequencies of clinical symptoms of transfusion complications will be ascertained. Recipient outcome data, when available, will be tabulated for different types of transfusion complications. Clinical characteristics of the cases that were reported to the blood bank before the study and after the study will be compared.

M. Timeline

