Appendix H: Interim Analysis

The statistical power for the study is based on several assumptions, including the estimated incidence of TRALI/Possible TRALI. Other assumptions include the number of units transfused per transfusion episode. Although these assumptions are based on validated processes, such as, the published literature and the pilot data generated during the design of LAPSII, there remains a small possibility that the actual data may not show the expected incidence of TRALI in the two groups under study. Therefore, an internal pilot study will be performed to re-assess sample size (Tim Friede and Meinhard Kieser. 2004. Sample size recalculation for binary data in internal pilot study designs, Pharmaceutical Statistics, vol 3 p269-279).

The internal pilot study will result in an interim analysis. The interim analysis will be performed when the recipient record review process has been completed (including the review by the Medical Board) for 33% of subjects. At this juncture, the incidence of TRALI (including possible TRALI) will be calculated without un-blinding cases and controls. The internal pilot study data will allow improved estimates of TRALI incidence, and component distribution per transfusion episode to be computed. The sample size calculation as described in section H.4.will be re-done.

If the interim analysis suggests that an increase in the number of study recipients is needed, then two potential approaches are available. First approach will explore the possibility of completing the study with the larger sample size. The second approach will explore the possibility of reducing the power of the study, e.g., from 90% to 85% to reduce the degree of increase in sample size so that the increase in the number is not overwhelming. The use of internal pilot study data to re-assess sample size may have a modest effect on statistical power (A.L. Gould and W.J. Shih. 1998. Modifying the design of ongoing trials without unblinding, Statistics in Medicine, vol 17, p89-100). Therefore, reducing power to a nominal 85% may result in the effective power being on the order of 80%. In any event, changing the sample size will not affect type I error (i.e. 0.05 level test for analysis), as the sample size re-assessment will maintain blinding.

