Appendix: I LEUKOCYTE ANTIBODY PREVALENCE STUDY – PHASE II

		TRALI (No risk	TRALI (with risk			TRALI/	OTHER*	
	STUDY ID	factors for ALI)	factors for ALI)	ALI	TACO	TACO	(Specify)	COMMENTS
1								
2								
3								
4								
5								
6								
7								
8								
9								
10								
11								
12								
13								
14								
15								

EXPERT REVIEW LOG FORM

* Other Specify E.g. Transient Obstruction, Bronchospasm, Accidental Extubation

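### F25 and G2 define Canadian possible TRALI differently, and under F25 the panel's single ALI category cannot supply it, contrary to F21

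*Protocol*

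**What the plan says.** **Objective.** C1 promises evaluation by both the Canadian and the NHLBI criteria. It places TRALI with other ALI risk factors inside the overall definition of TRALI.

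**Panel categories.** F21 begins its list "1. TRALI: classified by whether or not other risk factors for acute lung injury are present or not; 2. Acute lung injury (ALI"), followed by TACO, TRALI/TACO overlap and other. It then states: "These categories will allow cases to be grouped either by the Canadian Consensus Conference definition or the NHLBI Working Party definition". Appendix I, the "EXPERT REVIEW LOG FORM", has matching columns: TRALI without risk factors, TRALI with risk factors, ALI, TACO, TRALI/TACO, other, and comments. There is one ALI column.

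**Definitions.** The note to criterion 5 in F25 says that recipients who meet the criteria but have a "clear relationship to an alternate risk factor for acute lung injury will be considered to have possible TRALI". The same note admits such a case to the NHLBI category, TRALI with other risk factors, only "provided that the expert panel determines that transfusion is the most likely cause of the ALI". G2 describes the Canadian definition as one "which classified 'TRALI with other risk factors for ALI' as 'possible TRALI", with no judgement of cause.

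**Uses.** Section L asks for the incidence of TRALI and possible TRALI per unit and per recipient. When possible, it also wants ALI that cannot be told apart from TRALI, and "ALI that is not TRALI but that occurred within 6 hours or >6 hours of transfusion". At the interim in Appendix H, "the incidence of TRALI (including possible TRALI) will be calculated without un-blinding cases and controls".

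**The concern.** F25 is the section the panel applies. On its wording, Canadian possible TRALI is the wider group and NHLBI TRALI with other risk factors is a subset, separated by a causal judgement. The recording form keeps the subset and has no place of its own for the remainder. F21's assurance that the categories regroup to either definition is then true for NHLBI and untrue for the Canadian definition.

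At stake are the Canadian half of what C1 promises and the breakdowns in Section L. If the gap is found after adjudication, it can be closed only by a further panel review or by deriving the group from abstracted fields that the panel did not adjudicate.

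There is a second, smaller ambiguity. Appendix H names possible TRALI. Section L's primary Fisher test says only TRALI incidence. No sentence ties the two to the same set of cases.

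**Working it through.** **1. Map F25 onto the form.** Sort ALI cases that reach the panel by F25's own tests. Criteria 1 to 4 are new hypoxemia within six hours, bilateral infiltrates without left atrial hypertension (defined in criterion 3), and no pre-existing ALI.

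| Type | Description | Canadian (F25) | NHLBI (F25) | Log column |
|---|---|---|---|---|
| A | Criteria met, no alternate risk factor | TRALI | TRALI | TRALI, no risk factors |
| B | Criteria met, alternate risk factor, transfusion judged most likely cause | Possible TRALI | TRALI with other risk factors | TRALI, with risk factors |
| C | As B, but transfusion not judged most likely cause | Possible TRALI | Not TRALI | ALI (no other column fits) |
| D | ALI failing the criteria, e.g. pre-existing | Neither | Neither | ALI |

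The form yields A, B and the sum C + D.

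- NHLBI total and C1's overall definition: A + B, recorded.
- Canadian possible TRALI under F25: B + C. It cannot be formed, because C is not separable from D.
- Canadian possible TRALI under G2: B, recorded.

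F21's sentence is therefore right under G2 and wrong under F25, and the two sections cannot both stand. Section L's ALI breakdown needs C + D divided by onset and by likeness to TRALI. The log has no field for onset, pre-existing ALI or most likely cause.

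**2. Reproduce the design figure.** Inputs from Appendix D: 2.32% in case recipients, 0.79% in control recipients, 1,175 per arm, one-sided 0.05, exact conditional test.

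Power = Σ over (a, b) of Bin(a; n, p1) × Bin(b; n, p0), summed where the hypergeometric tail P(A ≥ a | a + b) ≤ 0.05.

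Result: 90.02% at 1,175, 85.00% at 1,007 and 80.02% at 886. All three entries in the 9.0% row of Table-12 are confirmed. The planning rates start from the 7 TRALI cases in 820 recipients of the planning study, with and without other risk factors, which corresponds to A + B.

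**3. Illustrate why the counted set must be named.** The documents give no count for type C. Assume that counting C adds the same rate x to both arms. One value can be tied to Table-2: 23 new bilateral infiltrates − 10 cardiogenic − 7 TRALI = 6, and 6/820 = 0.73%. The documents do not say what those 6 were, so this is only a point in a range.

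| x added to each arm | Power at 1,175 per arm | n per arm for 90% (steps of 25) |
|---|---|---|
| 0 | 90.0% | 1,175 |
| 0.25% | 85.2% | 1,375 |
| 0.5% | 80.4% | 1,550 |
| 0.73% | 76.5% | 1,725 |
| 1.0% | 72.4% | not computed |

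The blinded pooled rate would move from (2.32 + 0.79)/2 = 1.56% to 1.56 + 0.73 = 2.29% at x = 0.73%. H4 considers enlarging the study when incidence is low. A wider interim count would therefore make the sample look more adequate than it is for A + B.

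**The case against.** **G2 supplies the mapping, so the form is adequate.** This is the strongest reply. Under G2 the with-risk-factors column is the possible-TRALI group. It shows that the root of the matter is a conflict between G2 and F25, but it does not remove it. F25 carries the causal proviso and is what the panel is told to apply.

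**The primary comparison does not depend on possible TRALI.** This stands. C1 does not use the term, and its overall definition is the sum of two recorded columns.

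**The interim uses the planning set.** Largely fair. Appendix H opens by saying that power rests on the estimated incidence of TRALI/Possible TRALI, and that estimate came from the 7 planning cases with and without risk factors. A reader might infer that the interim and final analyses count different sets. The documents do not show that. They leave it open, because F25 gives possible TRALI a wider meaning.

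**Section L is conditional and other data exist.** Partly fair. The ALI breakdown is asked for only when possible, although the incidence of possible TRALI is not so qualified. Appendix G abstracts risk factors, pre-transfusion status, hypoxemia within six hours and timed blood gases, and the log has a comments column. A partial reconstruction may be feasible, but it would not be the blinded panel's judgement. The six-hour hypoxemia step in F4 also keeps much late ALI from the panel, so mixing with late cases is limited.

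**A further panel review would be unblinded.** A reader might fear this. Nothing in the documents supports it, since F21 has the panel work without knowledge of HLA status.

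**Conclusion.** The point holds as a conflict of definitions with a recording gap. F25 and G2 disagree on what Canadian possible TRALI is. Under F25, F21's regrouping statement is wrong, and the Canadian evaluation in C1 and the related breakdowns in Section L cannot be produced from adjudicated data. This rests on reading F25 as the operative criteria and on type C cases being logged as ALI, the only column that fits.

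C1's overall endpoint and its planned 90% power are not affected. The size of the gap is unknown because the documents give no count of displaced cases. The 72% to 85% range in the working is conditional on the wider set being counted and on an assumed equal addition of 0.25% to 1.0% to each arm. It shows why the set should be named and is not an estimate of harm.

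A reader might also infer a power loss by counting only cases without other risk factors. The documents do not support that reading. C1 and G2 include the risk-factor cases and those cases have their own column. Dropping them would also narrow the endpoint, whereas this gap would widen it.

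**What to change.** 1. Reconcile F25 with G2, so that possible TRALI has one stated meaning and the role of the causal proviso is explicit. Amend the regrouping sentence in F21 to match.
2. On the Expert Review Log, split the ALI column into (a) onset within six hours with an alternate risk factor, transfusion not judged most likely cause, and (b) other ALI, pre-existing or later onset. Alternatively, have the panel record alternate risk factor, onset within six hours, pre-existing ALI and most likely cause as separate items. Separate items would serve whichever reading step 1 adopts.
3. State in Section L and Appendix H that the primary Fisher test and the blinded interim incidence both count C1's set, TRALI without plus with other risk factors. Report Canadian TRALI plus possible TRALI as the second definition.

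The cost is one extra column or a few items on a form the blinded panel already completes, and a few sentences in F21, F25, G2, L and Appendix H. It is cheapest before adjudication begins, because later it means going back to cases already reviewed.
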